3.0 BACKGROUND AND RATIONALE

HER2 DEPENDENCY

HER2 is a member of the EGFR/ErbB family comprising 4 structurally related receptors: HER1 (EGFR), HER2, HER3, and HER4. HER receptors are normally activated by binding to specific ligands, resulting in a conformational change that allows formation of receptor homodimers and heterodimers. Receptor dimerization triggers autophosphorylation of specific tyrosine residues and activation of intracellular signaling pathways (1). HER2 is unique among HER family members in that it has no known ligand, and maintains a dimerization-ready conformation. HER2 is the preferred dimerization partner for other HER family members. HER2-containing heterodimers, particularly HER2/HER3, deliver the most potent growth signals (2).

The HER2 gene, which encodes a member of the erbB family of receptor tyrosine kinase, has been described as a key oncogenic driver in numerous malignancies. HER2 amplification is an oncogenic driver event which is found in approximately 20% of breast cancers and the successful application of HER2 targeted therapy in phase 3 randomized controlled trials has revolutionized the care and altered prognosis of these patients (5, 25, 27, 35, 36). Additionally, approximately 15-20% of gastroesophageal cancers are HER2 amplified and the addition of trastuzumab to chemotherapy in these patients was shown to improve overall survival (6). Databases from The Cancer Genome Atlas (TCGA), our institution and others have demonstrated HER2 amplifications in a variety of solid tumor cancers, including lung, bladder, endometrial and other cancers (Figure 1) (7-13, 37, 38). HER2 amplification occurs in 2-10% of lung cancers, 6% of bladder cancers, 5-12% of endometrial cancers and 2-5% of ovarian and colorectal cancers (7-15). High level HER2 protein overexpression by immunohistochemistry (IHC 3+) is a validated surrogate marker for gene amplification (4-6). HER2 amplification or HER2 overexpression in lung, bladder and endometrial cancers is associated with poor prognosis and these patients are in need of more effective systemic therapy (15-18).

[figure not shown]

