
6.0 CRITERIA FOR PARTICIPANT ELIGIBILITY

6.1 Participant Inclusion Criteria

1. Patients must be enrolled or agree to consent to the companion genomic profiling study MSKCC IRB# 12-245 Part A. Results are not required prior to

Memorial Sloan Kettering Cancer Center
[name]
[name]

initiating treatment on protocol, unless patients do not have other test results by IHC or FISH confirming HER2 overexpression.

2. Patients must have recurrent or persistent HER2 overexpressing endometrial cancer or endometrial carcinosarcoma. HER2 overexpression is defined as 3+ by IHC or 2+ with gene amplification by FISH (HER2/CEP17 ratio ≥ 2) or HER2 amplified (fold change ≥ 2) on MSK IMPACT.
3. Histologic documentation of diagnosis of endometrial carcinoma or carcinosarcoma is required.
4. Age ≥ 18 years
5. Patients must have had at least one but no more than two prior chemotherapeutic regimens for management of endometrial carcinoma (including neo-adjuvant and/or adjuvant chemotherapy). Initial treatment may include chemotherapy, chemotherapy and radiation therapy, and/or consolidation/maintenance therapy. Chemotherapy administered in conjunction with primary radiation as a radio-sensitizer WILL be counted as a systemic chemotherapy regimen. Prior hormonal therapy will **not** count as a prior regimen.
Prior treatment with trastuzumab is allowed.
6. Eastern Cooperative Oncology Group (ECOG) performance status of 0 or 1.
7. LVEF $\geq 50\%$ on baseline screening ECHO.
8. Resolution of adverse effects of recent surgery, radiotherapy, or chemotherapy to Grade ≤ 1 prior to first study treatment (with the exception of alopecia or clinically insignificant laboratory values).
9. Patients must have measurable disease. Measurable disease is defined by RECIST (version 1.1). Measurable disease is defined as at least one lesion that can be accurately measured in at least one dimension (longest diameter to be recorded). Each non-nodal lesion must be ≥ 10 mm when measured by CT, MRI or caliper measurement by clinical exam; or ≥ 20 mm when measured by chest x-ray. Lymph nodes must be ≥ 15 mm in short axis when measured by CT or MRI.
10. No active infection requiring antibiotics (with the exception of uncomplicated urinary tract infection).
11. All patients must consent to mandatory pre-treatment and post-treatment core needle biopsies.
12. Patients must have adequate hematological, liver, cardiac and kidney function within 14 days prior to first treatment:

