7. To examine ORR in each cohort by different types of molecular alterations, *HER2* amplification (by NGS and ISH separately), mutation and *HER2* overexpression, and assess their predictive value for response.

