14.0 BIOSTATISTICS

14.1 Populations for Analyses

All treated population: all treated patients regardless if they completed cycle 1 or the amount of drug received.

Efficacy population: All treated patients except patients without a post baseline assessment of response will be excluded.

Sample Size

This study aims to assess the activity of ZW25 in advanced HER2 overexpressing endometrial cancers and carcinosarcomas as measured by the best overall response rate as determined by RECIST 1.1. Assuming we use a binary endpoint of response, defined as best overall response of CR or PR versus not (best overall response \leq 24 weeks from the start of treatment), a sample size of 25 patients provides 90% power to test the hypothesis that the response rate is promising (defined as 30% or higher) against a non-promising rate of 10% or lower. This calculation is based on historical data from studies with ineffective agents in a similar patient population, which have ORR $<$ 10% and PFS rate at 6 months $<$ 20%,^{7,49-51} and uses a two-stage minimax Simon design, with Type I error=10%. Sixteen patients will be enrolled in the first stage and if 1 response is observed among the 16 the study will end for lack of activity. If \geq 2 responses out of 16 are observed, the study will continue to stage 2, where an additional 9 patients will be enrolled for a total of 25. At the end of the study, if at least 5/25 responses are observed then this will be considered a positive study (i.e. conclude that ORR is $>$ 10%).

Based on historical accrual rates in similar populations, and with the increased prior lines of therapy that will not be allowed for eligibility, we anticipate successful enrollment of 2 patients per month yielding a total accrual time of 18 months. Accrual will continue until 25 evaluable for efficacy response patients are treated (i.e. 25 patients in efficacy population as defined above).

Sensitivity analysis for ORR will include in the calculation of ORR patients who do not have post baseline assessment of response as failures.

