All patients will have their tumors molecularly profiled using the MSK-IMPACT platform, to evaluate for genomic alterations defined by MSK-IMPACT. Testing will (looking for presence/absence of genes at baseline and at end of study) be correlated to objective responses outcomes (binary covariates of CR or PR versus not) in an exploratory manner. Chi square or Fishers' exact test will be used to test this association. A subset analysis of patients who respond and then progress and have post progression material for molecular profiling will be performed in order to determine the mechanism(s) underlying acquired resistance. Specifically, we will be looking for presence of genetic alterations (at progression compared to baseline) which based on their understood biological mechanism may explain

acquired resistance. This analysis will be descriptive with the intention of understanding genetic alterations over time (at progression) and the types of mutation alterations among patients who respond and then progress. Patients will be followed up for a minimum of 12 months. Most variables above are binary (presence/absence) or expressed (yes/no) and they will be tested for association with response (yes/no) using Chi square or Fishers' exact test.

Serial pre- and post-treatment blood samples will be collected for cell-free tumor DNA analysis and sequenced using continuous quantitative methods (digital droplet PCR or hybridization capture next-generation sequencing) for the Rb, CD-K, PI3K- pathway alterations identified by pre-treatment and post-treatment tumor testing and descriptively correlated to clinical outcome. Binary covariates (presence/absence) will be tested for association with response (binary: CR or PR vs not) using Chi square of Fishers' exact test. Circulating tumor DNA is a continuous variable and these will be assessed descriptively for changes over time as part of exploratory aims.

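### The yes/no tests of HER2 amplification and overexpression against response are likely to tell little in a trial that enrols only HER2-positive patients; add a numeric HER2 comparison

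*Combined protocol and SAP*

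**What the plan says.** Exploratory objective 3 in Section 2.0 asks for response rate by type of molecular alteration: HER2 amplification (NGS and ISH taken separately), mutation and overexpression. Item 7 of the exploratory correlative studies in Section 10.0 repeats this and adds the aim to "assess their predictive value for response".

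Section 14.1 supplies the method. MSK-IMPACT alterations are coded as present or absent and related to response (CR or PR versus not) by Chi-square or Fisher's exact test, and a later sentence generalises: "Most variables above are binary (presence/absence) or expressed (yes/no) and they will be tested for association with response (yes/no". The section calls only ADA titers and circulating tumor DNA continuous, and both are handled descriptively. It names no analysis of a numeric HER2 value.

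Inclusion criterion 2 in Section 6.1 admits only HER2-positive patients: "HER2 overexpression is defined as 3+ by IHC or 2+ with gene amplification by FISH" (HER2/CEP17 ratio at least 2), or amplified on MSK-IMPACT (fold change at least 2). Section 3.0 adds: "High level HER2 protein overexpression by immunohistochemistry (IHC 3+) is a validated surrogate marker for gene amplification".

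**The concern.** A yes/no test needs patients on both sides of the cut. Here the same kind of cut decides who enters, so the marker-negative group may be very small. Patients who clear the cut may still differ widely in fold change or HER2/CEP17 ratio, and a presence/absence coding discards that information.

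At stake is how a null result is read. A non-significant Fisher test could be reported as evidence that HER2 level does not matter among HER2-positive patients, when the test had little chance of showing that it does.

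**Working it through.** **The plan's own figure.** Section 14.1 sizes the trial for the primary endpoint only: "a sample size of 25 patients provides 90% power to test the hypothesis that the response rate is promising (defined as 30% or higher". The null rate there is 10%, the design is Simon's two-stage minimax and the type I error is 10%; at least 2 of 16 responses are needed to continue and at least 5 of 25 for a positive study. The probability of a positive study is the sum over x = 2 to 16 of P(X = x | 16, p) × P(Y ≥ 5 − x | 9, p). This gives 0.0951 at p = 0.10 and 0.9030 at p = 0.30, so the stated design reproduces. No figure is given for the HER2 tests.

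**What can vary after entry.**
- Composite HER2 status: positive in everyone. Section 6.1 defines overexpression as this composite, so a yes/no variable on that definition is constant and Fisher p = 1.
- IHC, ISH and NGS taken singly: can vary, because criterion 2 is an either/or rule. However, two of its three routes require amplification, and Section 3.0 treats the third (IHC 3+) as a surrogate for it.
- HER2 mutation: not an entry criterion, so unaffected.

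**Negatives needed.** Inputs: n = 25 (Section 14.1); r responders, taken as 5 (the success threshold) and as 7 or 8 (either side of 30% × 25 = 7.5); k marker-negative patients, none responding; two-sided 0.05 (assumed, since Section 14.1 sets no level). The probability of that table is C(25 − k, r) / C(25, r), and the two-sided p adds every table no more probable. For r = 8, k = 8: 24,310 / 1,081,575 = 0.0225, and two-sided p = 0.026.

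| Responders | Largest k not significant | Smallest k significant |
|---|---|---|
| 8 | 7 (p = 0.057) | 8 (p = 0.026) |
| 7 | 8 (p = 0.057) | 9 (p = 0.027) |
| 5 | 10 (p = 0.061) | 11 (p = 0.046) |

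These rows cover only tables with no responder among the negatives. Others also reach p < 0.05: with 8 responders, 3 negatives all responding gives 0.024, and 11 negatives with 1 responding gives 0.042.

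**Fisher power by number of negatives.** Overall response rate is held at 30%, so the rate in positives is (7.5 − k × q) / (25 − k), where q is the rate in negatives. Power sums the two binomial probabilities over all tables with p ≤ 0.05.

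| Negatives k | q = 0 | q = 10% |
|---|---|---|
| 3 | 0% | 0.1% |
| 5 | 8.5% | 3% |
| 8 | 50% | 18% |
| 10 | 70% | 30% |
| 12 | 95% | 48% |

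**Numeric value against its yes/no version.** Simulations used n = 25, response rate about 30%, a logistic link, an odds ratio of 2 to 4 per SD and a value for all 25 patients. With 0 to 20% of patients below the cut (0 to 5 of 25), Fisher power was about 0 to 7% and exact rank-sum power about 25 to 73%. That range includes runs with the marker truncated at an entry threshold and the odds ratio taken per SD of the truncated values. With a truncated marker and 40% below the cut (10 of 25), the figures were 11 to 31% for Fisher and 33 to 72% for rank-sum. If truncation also weakens the effect per SD, both fall.

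**The case against.** A reader might infer that these tests cannot detect anything, or that no association will be found whatever the truth. The documents do not support that. Entry fixes only the composite. The qualifying result may come from any time before treatment (Section 9.0), while the research MSK-IMPACT is run on new biopsies. Section 3.0 reports heterogeneous expression in 53% of HER2-overexpressing serous tumors in a cited series, and lists outgrowth of HER2-negative cells under trastuzumab as a resistance mechanism; prior trastuzumab is allowed. A surrogate is not an identity. Marker-negative samples are plausible, and with enough of them Fisher's test has useful power.

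A reader might also infer that the numeric values are already in hand for everyone. That is firm only as a plan for MSK-IMPACT, which Section 14.1 intends for all patients but which depends on biopsies judged safe and feasible. Criterion 2 needs a FISH ratio only on the IHC 2+ route, and no section says that ratios or fold changes are captured for analysis.

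Finally, the quoted sentence says most variables and does not name HER2; the link comes from the objectives. Presence/absence coding is reasonable for the non-HER2 genes that it also covers, and the molecular work is labelled exploratory. All of this stands and limits the point. It does not supply a HER2 analysis for the case where discordance is low.

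**Conclusion.** The point holds in a limited form. Composite HER2 status cannot be tested at all, and the single-assay yes/no tests are likely to be uninformative unless roughly a third or more of the patients are negative on that assay (8 of 25 is 32%) and those patients rarely respond. Whether that happens is unknown, because the documents give no concordance between IHC, ISH and NGS. A numeric comparison had higher power in every simulated scenario, though modest at the smaller odds ratios. The power figures rest on an assumed two-sided 0.05 level, assumed effect sizes and complete numeric data. The matter is minor: the primary endpoint, sample size and stopping rule are untouched.

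**What to change.** In Section 14.1, for the HER2 markers:
- Cross-tabulate IHC, ISH and NGS status, so that the number of marker-negative patients per assay is visible.
- Compare MSK-IMPACT HER2 fold change, and HER2/CEP17 ratio where it was measured, between responders and non-responders by exact Wilcoxon rank-sum test, with AUC and confidence interval.
- Report response rate by IHC level.
- Record the numeric values in the database.
- Keep Fisher's test for alterations not used for entry, including HER2 mutation.

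The cost is a few lines of text and a few database fields, with no extra samples. The downside is that some numeric values will be missing, and the analysis stays exploratory with modest power.

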15.0 TOXICITIES/RISKS/SIDE EFFECTS

The treating investigator or qualified designee will assess each subject to evaluate for potential new or worsening AEs as specified in the Schedule of Assessments (see Section 10.0) and more frequently if clinically indicated. Adverse experiences will be graded and recorded throughout the study and during the follow-up period according to NCI CTCAE Version 5.0. Toxicities will be characterized in terms regarding seriousness, causality, toxicity grading, and action taken with regard to trial treatment.

ZW25 Monitoring and Management of Adverse Events

Infusion-related Reactions

Some patients treated with IV infusions of therapeutic drugs have experienced concurrent infusion-related reactions (see CTCAE Version 5.0). The signs and symptoms may vary and include for example, headache, fever, facial flushing, pruritus, myalgia, nausea, chest tightness, dyspnea, vomiting, erythema, abdominal discomfort, diaphoresis, shivers, lightheadedness, hypotension, palpitations, and somnolence. Anaphylaxis might occur at any time during an infusion.

While ZW25 is a fully humanized antibody, infusion reactions may occur. Infusion reactions consist of a symptom complex characterized by fever and chills, and may include nausea, vomiting, pain, headache, dizziness, dyspnea, hypotension, rash, and asthenia. Severe and potentially fatal reactions may include bronchospasm, anaphylaxis, angioedema, hypoxia, and severe hypotension. Infusion reactions may occur during or immediately following the initial infusion or at a later time point. While severe reactions usually occur during or immediate after infusion, onset and clinical course can be variable.

Prior to dosing with ZW25, all patients must receive prophylactic treatment for infusion reactions consistent with institutional standards that includes a corticosteroid. The

recommended regimen also includes acetaminophen orally, diphenhydramine (or equivalent) orally or IV 30 minutes through 60 minutes prior to infusion of ZW25 (recommended doses are: acetaminophen 650 mg, diphenhydramine 50 mg), and a corticosteroid (hydrocortisone, dexamethasone, or equivalent). If an alternative premedication regimen is thought to be required, approval from Zymeworks, Inc. should be sought. For patients who experience an infusion reaction despite initial premedication, additional prophylactic treatment may be added prior to subsequent doses, including an H2 blocker such as ranitidine as per institutional guidelines.

In the event of an infusion reaction, ZW25 infusion should be interrupted and medical therapy administered according to institutional standard of care (which, depending upon severity of the event, may include but not be limited to use of H1 and H2 inhibitors, corticosteroids, oxygen, IV fluids, epinephrine, and bronchodilators). Patients should be evaluated and carefully monitored until complete resolution of signs and symptoms. ZW25 should be discontinued in patients who experience a life-threatening (Grade 4) infusion reaction. Patients who experience a Grade 3 infusion reaction may be retreated at the discretion of the investigator at the next scheduled treatment. Such patients should receive additional prophylactic medication that may include a corticosteroid, and the duration of the infusion should be increased.

Infusions should be administered over 120 minutes through 150 minutes for the first 2 doses. If tolerated, infusion time may be reduced to 90 minutes for the next 2 doses, with reduction to 60 minutes for subsequent infusions at the discretion of the treating physician. Patients who experience a Grade 1 or Grade 2 infusion reaction may resume infusion of drug at a reduced infusion rate (30% through 50% slower than initial rate).

Samples will be collected from all treated patients for retrospective analysis to detect the presence of antibodies to ZW25 (i.e., ADA). In the event that an infusion reaction occurs or there is a suspicion of a hypersensitivity event, analysis of available samples collected to date for that patient may be performed.

Potential Cardiotoxicity

HER2 targeted therapies have been associated with cardiotoxicity. Therefore, only patients who have baseline normal left ventricular ejection fraction and no history of significant cardiac disease will be eligible for treatment with ZW25. Patients with a lifetime cumulative dose of anthracycline >300 mg/m² or who have received anthracycline treatment within 90 days of the expected first dose of ZW25 are not eligible for treatment.

Patients are monitored per the study-specific protocol for changes in cardiac function. Cardiac monitoring includes assessment of ECG (frequency and type of abnormalities using standard 12-lead ECG, including heart rate, PR interval, QRS complex, QTcF), and echocardiogram (estimation of ejection fraction).

Management of decreased left ventricular ejection fraction (LVEF), regardless of relationship to study drug, is described in Table 3 below.

Table 3: Management Guidelines for LVEF Dysfunction

Left Ventricular Dysfunction	Management
Symptomatic cardiac heart failure	
• Discontinue ZW25
LVEF <40%	
• Do not administer ZW25• Repeat LVEF assessment within 4 weeks• If LVEF <40% is confirmed, discontinue ZW25
LVEF below institutional limits of normal and \geq 10% points below pre-treatment baseline	
• Do not administer ZW25• Repeat LVEF assessment within 4 weeks• If the LVEF has not recovered to within 10% points from baseline, discontinue ZW25
LVEF 40% to \leq 45% and decrease is $<$ 10% points from baseline	
• Continue treatment with ZW25• Repeat LVEF assessment within 4 weeks
LVEF $>$ 45%	
• Continue treatment with ZW25, as applicable

Gastrointestinal Toxicity

The most common ZW25-related gastrointestinal TEAEs ($>$ 20%) were diarrhea and nausea. Two patients in Part 1/2 developed ZW25-related Grade 3 diarrhea (20 mg/kg), which subsequently resolved with medications. No patients in Part 3 developed ZW25 Grade 3/4 gastrointestinal toxicity.

Table 4: Management Guidelines for Potential Infusion-related Reactions

Infusion Reaction CTCAE v5.0 Severity Grade	Management
Grade 1: Mild, transient reaction	Maintain infusion rate unless progression of symptoms to \geq Grade 2; if symptoms worsen, refer to guidelines below Promethazine (or equivalent) 150 mg PO per day for nausea (or equivalent) Diphenhydramine (or equivalent) 25-50 mg PO or IV prn Methylprednisolone 125 mg (or equivalent) IV prn

Infusion Reaction CTCAE v5.0 Severity Grade	Management
Grade 2: Moderate	
Interrupt infusion and disconnect infusion tubing from patient
 
Promethazine (or equivalent) 150 mg PO per day for nausea
 
Diphenhydramine (or equivalent) 25-50 mg PO or IV prn
 
Methylprednisolone 125 mg (or equivalent) IV PRN
 
After recovery from symptoms, resume the infusion at 50% of the previous rate and if no further symptoms appear, gradually increase rate until infusion is completed.
 
For subsequent dosing in future cycles, patients should be pre-medicated with dexamethasone (or equivalent) 8 mg PO BID the day prior to drug administration and acetaminophen (or equivalent) 650 mg PO and diphenhydramine (or equivalent) 25-50 mg PO 30-60 minutes prior to dosing.

Grade 3: Severe, prolonged reaction not rapidly responsive to symptomatic medication and/or brief interruption of infusion; recurrence of symptoms following initial improvement; hospitalization indicated for clinical sequelae	
Immediately stop infusion and disconnect infusion tubing from subject
 
Administer diphenhydramine (25-50 mg) IV (or equivalent)
 
Administer IV steroids (methylprednisolone (or equivalent) up to 0.5mg/kg Q 6h) to treat ongoing reaction and prevent recurrence
 
Administer bronchodilators (nebulized albuterol/salbutamol, 2.5-5 mg in 3 mL of saline or equivalent) as medically indicated
 
Administer normal saline as medically indicated
 
Administer epinephrine (0.2-0.5 mL of a 1:1000 dilution (0.2-0.5 mg) SQ or IM) as medically indicated. Epinephrine should only be used if all other treatment methods fail to manage the infusion-related reaction.
 
Advise patient to seek emergency treatment and notify investigator/clinic if the infusion-related symptoms recur after discharge from clinic.
 
Report as a serious adverse event

Grade 4: Life-threatening consequences, urgent intervention indicated	Management as for Grade 3 reaction and permanently discontinue study medication treatment

Monitoring and Management of Diarrhea Following the Administration of Study Treatment: ZW25-associated Diarrhea

Mild to moderate diarrhea has been frequently reported in patients treated with ZW25. Patients will be prescribed loperamide as a prophylactic measure prior to Cycle 1 Day 1 of treatment and will be instructed on its use. Patient should be advised to contact their treating physician at the first sign of diarrhea and should be treated according to standard institutional practice. One suggested regimen would be the administration of 2-4mg of loperamide at the first sign of loose stool, with repeat dosing every 2 hours until symptoms resolve and up to a maximum of 16mg/day.⁴⁶ For Diarrhea that is G3 despite use of optimal anti-diarrheal treatment, hold drug until resolved to ≤ grade 1, then resume at a lower dose level.

Monitoring and Management of Nausea and Vomiting Following the Administration of ZW25

Nausea and vomiting have been reported in patients treated with ZW25. Patients should be advised to contact their treating physician at the first sign of vomiting or worsening nausea. Patients should be treated according to the American Society of Clinical Oncology (ASCO) Clinical Practice Guidelines for the use of antiemetics⁴⁷ outlined in Table 5.

Table 5: Management of Nausea and Vomiting

Severity Grade (CTCAE v5.0 Grade)	Management
Grade 1	Administer single 8 mg dose of dexamethasone before therapy
Grade 2	Administer a 5- HT ₃ receptor antagonist on day 1 (e.g. palonosetron, granisetron, or ondansetron) in combination with dexamethasone on days 1-3 or treat as per institutional guidelines. Aprepitant may be added to the combination.
Grades 3 and 4	Administer a neurokinin 1 receptor antagonist (e.g. aprepitant on days 1-3 or fosaprepitant on day 1), in combination with a 5-HT ₃ receptor antagonist on day 1 only, and dexamethasone on days 1-3 or 1-4 or treat as per institutional guidelines. For G3 nausea/vomiting despite optimal use of antiemetics, hold drug until resolved to ≤ grade 1, then resume at a lower dose level.

Other non-hematological toxicities: Except adverse events related to underlying disease, Grade 3 fatigue, isolated symptomatic G3 biochemistry abnormalities that last for < 7 days including electrolyte abnormalities that respond to medical intervention, for a Grade 3 event, hold study drug until resolved to ≤ Grade 1, then resume at lower level. For any grade ≥ 3 cardiac events and for Grade 4, non-hematological toxicities, permanently discontinue ZW25 treatment.

For any Grade 3 hepatic toxicity that does not resolve to baseline within 7 days, an abdominal CT scan must be performed to assess whether it is related to disease progression.

Re-treatment Criteria

To Begin a New Cycle of Treatment or continue treatment within a cycle

For a patient to begin a new cycle or continue a cycle of therapy, the following criteria must be met.

- ANC must be ≥ 1.0x10⁹/L (1,000/µL)
- Platelet count must be ≥ 75 x 10⁹/L (75,000/µL)

- All non-hematologic toxicities for which a causal association to study treatment cannot be ruled out, must be \leq Grade 1 (except alopecia) or returned to baseline.
- If the patient does not meet these criteria, dosing will be delayed and the patient should be re-evaluated within 48-72 hours. Dosing will resume if these criteria have been met.

If treatment is delayed due to treatment-related toxicity longer than one cycle, then the patient should be removed from study treatment. In such cases, continuation of study treatment may be considered for those patients who have experienced clinical benefit if agreed upon by the principal investigator and Zymeworks.

The use of granulocyte growth factors in accordance with ASCO guidelines may be implemented at the discretion of the treating physician.

Follow-up for AEs Leading to Discontinuation

Patients who discontinue study treatment for an AE or an abnormal laboratory value must be followed at least once a week for 4 weeks, and subsequently at 4-week intervals until resolution or stabilization of the adverse event or laboratory abnormality, whichever occurs first.

Dose Modification Guidelines

ZW25 Dose Reduction Following an AE

ZW25 dose may be reduced at the discretion of the Investigator after discussion with Zymeworks. Patients who develop adverse events requiring an interruption of ZW25 may resume treatment at a reduced dose level as shown in Table 6.

Table 6: ZW25 Dose Modification Guidelines

Regimen	If the patient was receiving ZW25 at:
Dose Level 1	20mg/kg intravenously (IV) every two weeks
Dose Level -1	15 mg/kg every two weeks
Dose Level -2	10 mg/kg every two weeks

**Reduction of the ZW25 dose below 10 mg/kg will not be permitted.*

Overdose and Medication Error

Overdose: There is no known treatment/antidote available for ZW25. Supportive measures should be instituted if an instance arises in which a patient suffers an overdose of any study drug.

Memorial Sloan Kettering Cancer Center
[name]
[name]

Medication Error: Zymeworks must be immediately notified in the event of error in prescribing, dispensing, administering and/or use of ZW25 or of any study drug, and the event must be reported on the eCRF.

If an error resulted in a serious adverse event, a Serious Adverse Event Report Form must be submitted within 24 hours of the event.

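### The Section 15.0 text and Table 4 give incompatible instructions for a Grade 1 infusion reaction, and leave the Grade 2 restart rate unclear

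*Combined protocol and SAP*

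**What the plan says.** Two places in Section 15.0 of the protocol govern what happens to the infusion when a patient reacts.

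The running text under Infusion-related Reactions gives a general rule: "In the event of an infusion reaction, ZW25 infusion should be interrupted and medical therapy administered according to institutional standard of care". It sets no grade threshold. Later in the same subsection it adds: "Patients who experience a Grade 1 or Grade 2 infusion reaction may resume infusion of drug at a reduced infusion rate", and puts the reduction at 30 to 50% relative to the initial rate.

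Table 4 gives rules by CTCAE grade. For Grade 1: "Maintain infusion rate unless progression of symptoms to" Grade 2 or above. For Grade 2: "Interrupt infusion and disconnect infusion tubing from patient", and after recovery "resume the infusion at 50% of the previous rate and if no further symptoms appear, gradually increase rate until infusion is completed".

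The infusion-reaction text does not refer to Table 4, and Table 4 does not refer back to the text. By contrast, the cardiotoxicity text points to Table 3 and the nausea and vomiting text points to Table 5. No sentence says whether text or table prevails.

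**The concern.** A nurse or physician facing a Grade 1 reaction is told in one place to stop the infusion and in another to leave it running at the same rate. For Grade 2 the two places describe the restart in different terms.

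Infusion-related reactions are a listed adverse event of special interest (Section 15.2.2) and one of the two most common treatment-related events in the protocol's own background data. Section 15.0 also requires each toxicity to be characterised by the action taken with trial treatment. The same mild event could therefore be recorded as an interruption for one patient and as no change for another, depending on which rule the staff read. The protocol-compliance audits in Section 16.3 would have no single standard for judging whether a deviation had occurred.

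**Working it through.** The plan states no figure on this point that could be reproduced. The check is a comparison by grade, followed by simple arithmetic.

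**Grade 1**
- Text: interrupt. Any resumption is at a reduced rate, 1 − 0.50 = 0.50 to 1 − 0.30 = 0.70 of the initial rate.
- Table 4: no interruption; 100% of the current rate while the reaction stays at Grade 1.
- The general sentence cannot be read as excluding Grade 1, because the later sentence names Grade 1 among the patients who may resume, and resuming presupposes a stop. The two instructions are incompatible.

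**Grade 2**
- Interruption: both places require it.
- Restart rate: 50 to 70% in the text, 50% in Table 4. The table's value is the slow end of the text's range.
- Reference rate: *initial* in the text, *previous* in Table 4.
- Re-escalation: not mentioned in the text; gradual increase in Table 4.

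**Why the reference rate can matter.** "Infusions should be administered over 120 minutes through 150 minutes for the first 2 doses"; later doses may be shortened in steps to 60 minutes. For illustration, assume a 250 mL bag (the example volume under Administration in Section 5.1) and a 120-minute first dose.
- First dose: 250 mL / 2 h = 125 mL/h. Text: 0.50 × 125 = 62.5 to 0.70 × 125 = 87.5 mL/h. Table 4: 0.50 × 125 = 62.5 mL/h, then rising. The restart rates are compatible.
- Later 60-minute dose: 250 mL / 1 h = 250 mL/h. Table 4: 0.50 × 250 = 125 mL/h. Text, if *initial* means that infusion's own starting rate: 0.50 × 250 = 125 to 0.70 × 250 = 175 mL/h, compatible. Text, if *initial* means the first-dose rate: 62.5 to 87.5 mL/h, which does not include 125.

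Compatibility at Grade 2 therefore depends on a word that the protocol does not define.

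**How many patients.** The background in Section 3 gives two rates of treatment-related infusion reaction:
- 34% in the 43-patient update, where the most common related events were all Grade 1 or 2: 0.34 × 25 = 8.5.
- 40.3% among the 67 patients in Parts 1 and 2 of the phase 1 study: 0.403 × 25 = 10.1. The related events listed at Grade 3 or higher there do not include an infusion reaction.

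Both figures count infusion reactions without separating Grade 1 from Grade 2. The number meeting the Grade 1 conflict could be anything from none to about 10.

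**The case against.** The best defence is that the two places work at different levels. The text is a general statement that leaves treatment to institutional standard of care according to severity, and Table 4 is the grade-specific guideline, so a sensible reader would follow the table. The trial is also single-centre, which limits variation in practice. Both places agree on permanent discontinuation at Grade 4, and neither provides for resuming the same infusion after Grade 3, so the disagreement is confined to the mildest reactions.

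Part of this stands: the practical risk is modest. It does not remove the Grade 1 mismatch. The severity qualifier in the text attaches to the choice of medical therapy and not to the interruption, and neither place is made subordinate to the other.

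The defence is stronger on Grade 2. A reader might infer that the Grade 2 rules also contradict each other. The documents do not support that. Both interrupt, the text is permissive (patients *may* resume), Table 4's 50% lies within the text's range if the two reference rates are the same, and the text's silence on re-escalation is not an instruction against it.

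A reader might also infer that 8 to 10 patients will meet conflicting rules. That goes too far:
- There is no grade split.
- Section 15.0 notes that reactions can occur after the infusion, when rate rules no longer apply.
- The rates come from mixed-tumour phase 1 populations, one of them spanning several doses and schedules, and may not carry over.

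**Conclusion.** The Grade 1 contradiction is real and rests on the wording alone. The Grade 2 instruction is ambiguous in its reference rate and in whether the rate may be raised again, but it is not contradictory.

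As to size, if the phase 1 rates apply to 25 patients, about 8 to 10 with any related infusion reaction is a rough upper figure for those affected. The number meeting the Grade 1 conflict cannot be derived from the documents.

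The consequence is inconsistent handling of mild reactions and inconsistent entries for action taken. It might be tempting to go further and say that event grades or the safety tables would be distorted. The documents show no route by which these rules would change a grade, and Section 14 plans only a tabulation of adverse events by CTCAE, with no summary of infusion interruptions. Response assessment, sample size, error rates and the primary analysis are untouched. The point should be corrected as an internal inconsistency in a safety instruction; it is not a flaw in the statistical design.

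**What to change.** Reconcile the Infusion-related Reactions text in Section 15.0 with Table 4 so that each grade has one instruction covering four items: whether the infusion is interrupted, the restart rate, the rate to which that percentage refers, and whether and how the rate may be increased afterwards. State it identically in both places, or state it once and cross-refer, as is done for Tables 3 and 5. If *initial* or *previous* is kept, define it, given that infusion times shorten over successive doses. The clinical team must decide which rule stands; this review takes no position on that.

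The cost is protocol wording only, with no change to the sample size, assessments or analysis.
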